### **8.6.2. Adverse Events**

Clinical and laboratory adverse events (AEs) will be coded using the Medical Dictionary for Regulatory Activities (MedDRA). System Organ Class (SOC), High-Level Group Term (HLGT), High-Level Term (HLT), Preferred Term (PT), and Lower-Level Term (LLT) will be attached to the clinical database.

Summaries (number and percentage of subjects) of treatment-emergent (TE) AEs (by SOC and PT) will be provided by treatment group:

- All TEAEs
- TEAEs of Grade 3 or higher
- TEAEs of Grade 2 or higher
- All TE treatment-related AEs
- TE treatment-related AEs of Grade 3 or higher
- TE treatment-related AEs of Grade 2 or higher
- All TE SAEs
- All TE treatment-related SAEs
- All TEAEs leading to premature discontinuation of any study drug
- All TEAEs leading to temporary interruption of any study drug

All AEs collected during the study will be presented in the data listings.

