#### 7.1.6. Summaries of Adverse Events and Deaths

AEs will be summarized based on the Safety Analysis Set.

3 sets of summaries will be generated: (1) all TEAEs for 12 Week Regimen (2) all TEAEs for 48 Week Regimen (Group 1-3, and 5). (3) all AEs during TFFU period (AEs that occur during TFFU after Week 48) will be listed, and summary tables will be presented using the TFFU Analysis Set as appropriate.

A brief, high-level summary of the number and percentage of subjects who experienced at least 1 TEAE in the categories described below will be provided by treatment group. All deaths observed in the study will also be included in this summary.

The number and percentage of subjects who experienced at least 1 TEAE will be provided and summarized by SOC, PT and treatment group:

- TEAEs (with severity)

For the AE categories described below, summaries will be provided by PT and treatment group:

- TEAEs
- TEAEs of Grade 3 or higher
- TE treatment-related AEs
- GS-9992 only TE treatment-related AEs (Group 1, 3-5)
- TE treatment-related AEs of Grade 3 or higher
- TE SAEs
- TE treatment-related SAEs
- TEAEs leading to premature discontinuation of GS-9992
- TEAEs leading to premature discontinuation of TAF
- TEAEs leading to dose modification or temporary interruption of GS-9992
- TEAEs leading to dose modification or temporary interruption of TAF

Multiple events will be counted only once per subject in each summary. Adverse events will be summarized and listed first in alphabetic order by SOC and then by PT in descending order of total frequency within each SOC. For summaries by severity grade, the most severe grade will be used for those AEs that occurred more than once in an individual subject during the study.

In addition to the by-treatment summaries described above, data listings will be provided for the following AEs:

- All AEs, indicating whether the event is treatment-emergent
- All AEs of Grade 3 or higher
- SAEs
- All deaths
- AEs leading to premature discontinuation of any study drug
- AEs leading to dose modification or temporary interruption of any study drug

For subjects in the TFFU Analysis Set, by-subject listings will be provided as follows:

- All AEs
- AEs of Grade 3 or higher
- All SAEs
- All deaths

The listings will indicate whether an event is treatment-emergent, and whether the event occurred during TFFU.

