## **7.7. Changes From Protocol-Specified Safety Analyses**

There are no deviations from the protocol-specified safety analyses.

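### SAP 7.7 declares no change to the safety analyses, yet SAP 7.1.6 drops the protocol's pooled any-study-drug discontinuation and interruption summaries, so only TAF stopping is compared with the TAF-alone group

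*SAP*

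**What the plan says.** Protocol 8.6.2 sets the level of presentation for its whole list of adverse event categories: "Summaries (number and percentage of subjects) of treatment-emergent (TE) AEs (by SOC and PT) will be provided by treatment group". The list includes "All TEAEs leading to premature discontinuation of any study drug" and "All TEAEs leading to temporary interruption of any study drug". It also includes "TEAEs of Grade 2 or higher", together with a treatment-related version of that category.

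SAP 7.1.6 gives one table of all TEAEs by SOC and PT with severity. For the remaining categories it says: "For the AE categories described below, summaries will be provided by PT and treatment group". Those categories include "TEAEs leading to premature discontinuation of GS-9992" and "TEAEs leading to premature discontinuation of TAF", and a matching pair, one per drug, that combines dose modification with temporary interruption. The high-level summary in the same section uses the same categories. The pooled any-drug wording appears only in the by-subject listings.

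SAP 7.7, the section for declaring changes to the safety analyses, reads in full: "There are no deviations from the protocol-specified safety analyses".

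**The concern.** Safety and tolerability of the 12-week regimens is a primary objective, and Group 1 versus Group 2 is the only randomised comparison. A natural descriptive question is how many subjects in each group had an adverse event that made them stop or interrupt any part of their regimen. The protocol promised that figure by treatment group. The SAP does not produce it as a summary.

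The disclosure matters separately. SAP 6.4, the parallel section for efficacy, does report a change (the pharmacokinetic analysis that was not done). A reader will therefore take SAP 7.7 as a positive assurance that the protocol's safety summaries are all present.

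**Working it through.** The plan gives no figure to reproduce here. The check is a comparison of the two table lists, followed by a bound on what can be recovered.

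**Step 1. The lists side by side.**

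| Item | Protocol 8.6.2 | SAP 7.1.6 |
|---|---|---|
| AE-driven discontinuation | One summary, pooled over drugs | Two summaries: GS-9992; TAF |
| AE-driven interruption | One summary, pooled, interruption only | Two summaries, per drug, dose modification added |
| Grade 2 or higher | All-cause and treatment-related | Neither listed |
| Level | SOC and PT throughout | SOC and PT for all TEAEs; PT for the other categories |

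For discontinuation and interruption, pooled summaries number 2 in the protocol and 0 in the SAP. Per-drug summaries number 0 and 4.

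**Step 2. Which groups can enter each SAP row.** SAP 3.1.2 names GS-9992 and TAF as the study drugs. GS-9992 is given in Groups 1, 3, 4 and 5, and TAF in Groups 1, 2, 3 and 5. Group 2 is therefore structurally zero in the two GS-9992 rows. Only the two TAF rows can hold events in both the combination groups and the TAF-alone group.

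**Step 3. Who is missing from the shared rows.** A subject in Group 1, 3 or 5 who stops GS-9992 for an adverse event and continues TAF is not in the TAF row. The protocol's ALT tables manage the two drugs separately, so this can happen:
- For confirmed ALT at or above 10 × ULN without hepatic toxicity, Table 7-1 raises reduction or discontinuation of GS-9992, while Table 7-2 continues TAF.
- For ALT above 2 × nadir with hepatic toxicity, Table 7-1 discontinues GS-9992, while Table 7-2 takes up stopping TAF only from 10 × ULN.

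The omission runs one way. In the combination groups the TAF row can be at most equal to the any-drug count, whereas in Group 2 the two are identical.

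**Step 4. Can the any-drug count be rebuilt from the SAP rows?** Let g be the subjects stopping GS-9992, t those stopping TAF, n the group size and u those stopping any study drug. One subject may be in both rows, so

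max(g, t) ≤ u ≤ min(n, g + t).

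With the planned Group 1 size of n = 30 and counts assumed for illustration:
- g = 3, t = 1: u is 3 to 4, that is 3/30 = 10.0% to 4/30 = 13.3%.
- g = 4, t = 1: u is 4 to 5, that is 13.3% to 5/30 = 16.7%.
- g = 3, t = 3: u is 3 to 6, that is 10.0% to 6/30 = 20.0%.

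The rows bound the figure but do not fix it. The same bound applies to interruption, with the added point that the SAP rows mix in dose modification, so the protocol's interruption-only category cannot be isolated either.

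**Step 5. Do other outputs supply it?** The disposition summary in SAP 4.1 also splits completion status and reasons for stopping by drug. The SAP 7.1.6 listings keep the pooled category by subject, so a hand count is possible. Those listings cover AEs, not only treatment-emergent ones, so the 12-week and 48-week windows of SAP 7.1.5.1 must be applied in making the count.

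**The case against.** The case on the other side is substantial, and several parts of it stand.

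- **A control comparison exists.** A reader might infer that no SAP row compares AE-driven stopping with TAF alone. That is too broad. The TAF discontinuation and TAF modification/interruption tables are by treatment group and do compare TAF stopping across Groups 1, 2, 3 and 5. What is missing is a row for stopping any study drug.
- **The direction need not be lost.** A reader might infer that the apparent direction of the comparison depends on which row is read. The high-level summary puts the rows side by side. With g = 4 and t = 1 in Group 1 and one TAF stop in Group 2, the any-drug figure is 13.3% to 16.7% against 1/10 = 10.0%, so the direction is recoverable in that example. With 10 subjects in Group 2, one event moves the rate by 10 points in any case.
- **The merged category captures more.** Adding dose modification brings in GS-9992 reductions that the protocol's interruption row would miss. It is a sensible extension, but still an undeclared change.
- **SOC information is not wholly absent.** SAP 7.1.6 also says that adverse events are ordered by SOC and then PT, which conflicts with its own PT-only sentence. The all-TEAE table has SOC counts with severity, and the high-level summary gives subjects per category. This is partly an inconsistency to settle.
- **The listings allow an exact count** in a study of about 120 subjects.

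None of this makes the SAP 7.7 statement true, and a hand count from a listing does not replace a summary that the protocol specified.

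**Conclusion.** The point holds as a disclosure and reporting fault. SAP 7.7 is wrong as written: two pooled summaries were replaced by four per-drug ones, interruption was merged with dose modification, category tables were set by PT, and the Grade 2 or higher summaries were dropped, all without declaration. No summary row compares AE-driven stopping or interruption of any study drug between GS-9992 plus TAF and TAF alone.

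The size is limited. SAP 3.5 and 6.1.2 rule out hypothesis testing and the sample size has no power basis, so nothing inferential changes. The event counts used above are assumptions. How much the TAF row understates stopping depends on how many subjects stop GS-9992 alone for events recorded as AEs, which the documents do not predict.

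Two further readings are not supported. The protocol evaluates safety by laboratory tests and adverse events and does not rank AE-driven stopping as the main tolerability measure. The Group 5 hold rule in Protocol 6.11 counts by SOC, but it operates during dosing and does not run on these tables.

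**What to change.** In SAP 7.1.6, for both the 12 Week and 48 Week Regimen analyses, add two categories to the high-level summary and the tables:
1. The protocol's pooled discontinuation category, "All TEAEs leading to premature discontinuation of any study drug".
2. A pooled category for AE-driven dose modification or interruption, counting each subject once across both study drugs.

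Keep the per-drug rows as supplements. Settle whether the category tables are by PT or by SOC and PT, so that the PT-only sentence, the SOC-then-PT ordering and Protocol 8.6.2 agree. In SAP 7.7, replace the current sentence with a list of every protocol-specified safety summary that is changed or not restored, including the Grade 2 or higher summaries and the widening of interruption to dose modification. If the SAP is already final, its Introduction says later changes are documented in the clinical study report, and the list belongs there.

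The cost is SAP wording and a few table shells. The any-drug listings and the any-drug wording in the TEAE definitions of SAP 7.1.5.1 already need the underlying flags, so no new data are required.

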## **8. PHARMACOKINETIC ANALYSES**

PK samples were collected and stored at Covance. A decision was made that PK analysis will not be performed.

## **10. SOFTWARE**

SAS® Software Version 9.4. SAS Institute Inc., Cary, NC, USA.

## 11. SAP REVISION

Revision Date (DD MMM YYYY)	Section	Summary of Revision	Reason for Revision

## 12. APPENDICES

[Appendix 1. Schedule of Assessments](#)

**Appendix 1. Schedule of Assessments**

Procedures	Screening (45 days)	Baseline Day 1	Weeks ( $\pm$ 3 Days)									Early Discontinuation a	24 Week Treatment-Free Follow-up ( $\pm$ 5 Days) (End of Weeks 4, 8, 12, 16, 20, and 24)	
			1	2	4	8	12	16	24	36	48			
Informed Consent (at, or prior to, screening visit) n	X													
Review of Inclusion/ Exclusion Criteria	X	X												
Medical History	X	X												
AEs and Concomitant Medications	X	X	X	X	X	X	X	X	X	X	X	X	X	X c
Complete Physical Examination	X	X					X						X	X c
Symptom-directed physical examination b			X	X	X	X		X	X	X	X			X
Height	X													
Body Weight	X	X					X				X	X		
Vital Signs d	X	X	X	X	X	X	X	X	X	X	X	X	X	X
12-lead ECG e	X	X					X						X	
Pregnancy Test f	X	X	X	X	X	X	X	X	X	X	X	X	X	X c
Urinalysis	X	X	X	X	X	X	X	X	X	X	X	X	X	
Urine Drug Screen	X	X												
Safety laboratory tests (hematology and chemistry, Coagulation Panel	X	X	X	X	X	X	X	X	X	X	X	X	X	X
Quantitative plasma	X	X	X	X	X	X	X	X	X	X	X	X	X	

Procedures	Screening (45 days)	Baseline Day 1	Weeks (± 3 Days)									Early Discontinuation a	24 Week Treatment-Free Follow-up (± 5 Days) (End of Weeks 4, 8, 12, 16, 20, and 24)	
			1	2	4	8	12	16	24	36	48			
HBV DNA														
FibroScan	X													
HCC imaging	X													
Quantitative serum HBsAg, CCI	X	X	X	X	X	X	X	X	X	X	X	X	X	X
Qualitative HBV serology g	X	X					X		X	X	X	X	X	X
Collection of PBMC, whole blood, serum, and plasma samples for biomarker analysis		X	X		X			X		X		X	X	X h
HBV Genotyping o		X												
Serum sample for HBV viral sequencing (resistance surveillance) or ddPCR p	X	X	X	X	X	X	X	X	X	X	X	X	X	X
Single Plasma PK j			X	Xi	X	Xi	X	X	X	X	X	X	X	
CCI														
Other Viral Serology(HCV, HIV, HDV) l	X													
Creatinine Clearance	X	X					X					X	X	
Randomization		X												
Dispense TAF		X			X	X	X	X	X	X				
Dispense GS-9992		X			X	X								
In-Clinic Dose with GS-9992		X		X m	X m	X m								

Procedures	Screening (45 days)	Baseline Day 1	Weeks (± 3 Days)									Early Discontinuation a	24 Week Treatment-Free Follow-up (± 5 Days) (End of Weeks 4, 8, 12, 16, 20, and 24)	
			1	2	4	8	12	16	24	36	48			
In-Clinic dose with TAF		X												
GS-9992 Accountability			X	X	X	X	X						X	
TAF Accountability			X	X	X	X	X	X	X	X	X	X	X	

**CCI**

- a. The Early Discontinuation (ED) visit should be performed within 14 days from notification of study discontinuation.
- b. Symptom directed physical exam will only be performed when subject is experiencing symptoms.
- c. To completed at Treatment Free Follow up Week 4 only: AE review, complete physical examination, and urine pregnancy test.
- d. Vital signs include blood pressure, pulse, respiration rate and temperature.
- e. QTc interval will be reported using Fridericia’s correction: QTcF QT/RR0333. Subjects must rest quietly in the supine position for a minimum of 5 minutes prior to the recording.
- f. For female subjects of childbearing potential, the serum pregnancy test will be performed at Screening. Urine test will be performed at all other visits as indicated. Positive urine test will be confirmed with serum test. Pregnancy testing should include prevention counseling.
- g. Qualitative HBV serology: (HBeAg [reflex HBeAb if HBeAg is negative] and HBsAg [reflex HBsAb if HBsAg is negative]). Collected every 12 weeks during the study. Post Treatment visit Weeks 12 and 24.
- h. PBMCs to be collected at Weeks 4, 8, 12, and 24 only. PBMC sample collection is only required at the sites that have access to PBMC processing laboratory.
- i. Weeks 2 and 8 PK samples will be collected between 15 minutes and 4 hours post dose. **CCI**
- j. Single PK sample will be collected at any time on all other Post Day 1 visits **CCI**. For Group 4, single PK will be collected through Week 12 only.
- k. **CCI**
- l. In the event of a positive result and/or antigen testing for HIV, HDV, or HCV serology, reflex tests will automatically be performed.
- m. In clinic dose required for Weeks 2 and 8 single PK samples **CCI**
- n. **CCI**
- o. HBV genotyping for Groups 1 3 and 5 only, for Group 4 historic genotype should be documented in EDC if available.
- p. Serum sample collected will be used for HBV viral sequencing and possible phenotypic analyses for all groups or ddPCR for Group 4.

